**Table 7. Causality Assessments**

Classification	Causality Criteria	Causal Association
Probably Associated	

• An AE that follows a strong temporal relationship to the administration/use of the study product and/or recurs on rechallenge.

• Results in a positive sensitivity test.

• Unlikely to be attributed to disease, procedure or other drugs/devices.

• An AE improves with withdrawal of the product.

	Yes
Possibly Associated	

• An AE follows a reasonable temporal relationship to the administration/use of the study product.

• An alternative etiology is equal or less likely.

	Yes
Unlikely Associated	

• An AE has little or no temporal relationship to the administration/use of the study product.

• An alternative etiology is more likely.

	No
Not Associated	

• An AE that is due to underlying or concurrent illness, complications, concurrent treatments or effect of another concurrent device/drug and is not associated to the device/drug, that is, does not follow a reasonable temporal relationship to administration/use of the study product.

• Has a much more likely alternative etiology.

	No

**Table 8. Severity Assessments**

Criterion	Definition
Mild	Is a transient discomfort and does not interfere in a significant manner with the patient's normal functioning level. The AE resolves spontaneously or may require minimal therapeutic intervention.
Moderate	Produces limited impairment of function and can require therapeutic intervention, but produces no sequelae.
Severe	Results in a marked impairment of function and can lead to temporary inability to resume usual life pattern. The AE produces sequelae requiring (prolonged) therapeutic intervention.

**Table 9. Outcome Conclusion Criteria**

Fatal
Not recovered/Not resolved/Permanent: This outcome is reached for AEs which are ongoing when the patient's end of study is due to death related to another AE
Recovering/Resolving: This outcome is reached for AEs which are ongoing at the patient's end of study
Recovered/Resolved with Sequelae: If there are some residual effects caused by the event
Recovered/Resolved
Unknown

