If an AE or DD occurs, a full description of the event should be recorded including the date and time of onset, as well as outcome, seriousness, severity, event description, actions taken, and causal relationship of the AE. Investigators should review and reference the causality (see [Table 7](#)) and severity definitions (see [Table 8](#)) when determining relationship of the AE to the study product or typical PD therapy. The Investigators may also discuss the event(s) with the Baxter Medical Monitor or designee.

All AEs should be actively solicited and documented in the eCRFs, no matter how common they are for a particular patient and regardless of the causality assigned by the Investigator. Additionally, any AE voluntarily reported by the patient should be recorded and verified by the Investigator or a designee with the relevant source documents and eCRF. Each SAE will be documented on a separate SAE report form.

The outcome/ resolution of all AEs will be determined by the Investigator and documented in the AE eCRF. Investigators will be instructed to follow all treatment emergent AEs as follows: Adverse device effects (related AEs) and all SAEs (related or not) will be followed until resolution or stable, including following the patient after the end of the study if necessary.

For the outcome conclusions that can be used on the eCRF by the Investigator, refer to [Table 9](#).

---

If a patient in this study also receives a Baxter medicinal/ drug product which is part of a patient's normal treatment (not an investigational product or comparator), any AE which is considered causally related to the medicinal/ drug product by either the Investigator or the medical monitor shall be forwarded by the Investigator or a designee within 24 hours of becoming aware of the AE to Baxter Global Patient Safety

( [REDACTED] ) for assessment as per Baxter's process for case processing of spontaneous reports.

Causality is a determination of whether there is a reasonable possibility that the study product is etiologically related to/ associated with an AE. Causality assessment includes, for example, assessment of temporal relationships, dechallenge/rechallenge information, association (or lack thereof) with underlying disease, presence (or absence) of a more likely cause, and physiologic plausibility.

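### Table 9 codes an adverse event still open when a surviving patient leaves the study as recovering, whether it is improving, unchanged or worsening

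*Protocol*

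**What the plan says.** Protocol Section 7.2 leaves the outcome of each AE to the investigator and points to a fixed list: "For the outcome conclusions that can be used on the eCRF by the Investigator, refer to" Table 9.

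Table 9 has six entries. Two of them define an outcome for an event that has not ended:

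- "Recovering/Resolving: This outcome is reached for AEs which are ongoing at the" patient's end of study.
- *Not recovered/Not resolved/Permanent*, for events "ongoing when the patient's end of study is due to death related to another AE".

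The other four are *Fatal*, *Recovered/Resolved*, *Unknown* (listed without a definition), and "Recovered/Resolved with Sequelae: If there are some residual effects caused by the event".

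Section 7.2 also has adverse device effects, and all SAEs whether related or not, followed until they resolve or are stable, past the end of the study if needed. No such rule is given for non-serious, unrelated events. Protocol Sections 8.9 and 8.10 place the last assessment 5-10 days after the last study treatment.

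In the SAP, Section 14.2.1 makes outcome one of the items in the AE listings. Neither Section 14.2.4 nor the table list in Section 17 contains a summary by outcome.

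Severity is graded by protocol Table 8. Moderate is "Produces limited impairment of function and can require therapeutic intervention, but produces no sequelae". Severe is marked impairment of function, and its definition goes on to say "The AE produces sequelae requiring (prolonged) therapeutic intervention". SAP Section 14.2.4 tabulates treatment-emergent AEs and SAEs by severity.

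**The concern.** An outcome code should tell the reader what had become of the event when it was last seen. Table 9 assigns the code by how the patient's participation ended, so label and rule can disagree. An event may be called permanent only if the patient dies of something else, and a survivor whose event is static or deteriorating is recorded as getting better.

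The safety profile is a secondary endpoint of a single-arm study. No comparator group, coded under the same rule, is available to show that the outcome column is uninformative for open events. Open events at the last visit are also foreseeable: a patient may be withdrawn because of an AE (protocol Section 3.5.1), and the closing visit comes only 5-10 days after the last treatment.

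**Working it through.** No arithmetic applies. The check sets the definitions side by side.

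**Step 1. Which Table 9 code does an open event receive?**

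| Direction at last observation | Patient survives to end of study | Study ends by death related to another AE |
|---|---|---|
| Improving | Recovering/Resolving | Not recovered/Not resolved/Permanent |
| Unchanged | Recovering/Resolving | Not recovered/Not resolved/Permanent |
| Worsening | Recovering/Resolving | Not recovered/Not resolved/Permanent |

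The rows within each column are identical, so the event's direction plays no part in the code. For survivors, two of the three rows carry a label that contradicts the event. In the death column, the improving row is mislabelled the other way.

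**Step 2. Could another code serve a survivor's unresolved event?** *Fatal* and *Recovered/Resolved* do not apply. *Recovered/Resolved with Sequelae* says that the event itself is over. *Unknown* has no definition and does not suit an event whose state is known. No other entry fits.

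**Step 3. For which events is the code final?**

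- Non-serious, unrelated events: no follow-up is stated beyond the closing visit, so the code given there stands. New edema, judged non-serious and unrelated to the product and unchanged at that visit, would be recorded as recovering.
- Adverse device effects and SAEs: follow-up continues until they resolve or are stable. Stable is not a Table 9 outcome, and the protocol does not say whether the code is revised.

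**Step 4. Where does the code go?** Under the SAP it goes to the AE listings only. AE counts and rates do not use it. Seriousness is defined separately in protocol Table 5. *Fatal* is a code of its own and is untouched by the problem.

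**Step 5. Table 8, cross-classified and read as written.**

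| Impairment of function | No sequelae | Sequelae |
|---|---|---|
| Not significant | Mild | At odds with Mild, which is described as transient |
| Limited | Moderate | No grade: Moderate excludes sequelae, Severe needs marked impairment |
| Marked | No grade: Moderate needs limited impairment, Severe states sequelae | Severe |

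Three of the six combinations have a clear grade. Of the two with none, marked impairment without sequelae might be graded down and limited impairment with sequelae might be graded up.

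**The case against.** The strongest reply is that little depends on the label. The same listings show the AE end date, and SAP Section 16.2.3 says that stop dates are not imputed, so an open event can be recognised whatever its outcome code. Worsening in severity is not lost either: protocol Section 7.2 keeps the highest grade, and SAP Section 14.2.1 lists each severity when it changes. The primary endpoints are solution and water tests. All of this stands, and it limits the reach of the point. It does not make the outcome entry correct: a missing end date shows that an event is open, not whether it was improving.

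It can also be said that the investigator determines the outcome and that Table 9 lists conclusions that can be used. The wording is permissive, but an investigator who chose the not-recovered code for a survivor would be departing from the only definition given for it.

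Three stronger readings are tempting and are not supported:

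- *Every open event is coded as improving.* Table 9 itself excepts events open at death related to another AE. For device effects and SAEs followed later, a lasting wrong code is an assumption, because the documents are silent on updating.
- *Table 8 under-counts severe events, so both tables favour the product.* Marked impairment does not meet Moderate, so a downgrade is a risk and not a consequence. Limited impairment with sequelae could move the other way. A grade left blank is set to severe by SAP Section 14.2.1, although that rule would not correct a wrong grade that had been entered.
- *Serious events are made to look less serious.* Seriousness rests on Table 5. Hospitalization alone makes an SAE, whatever the Table 8 grade or Table 9 outcome.

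**Conclusion.** The Table 9 defect is real and follows from its wording. In survivors, every direction of an open event maps to the recovering code, and the not-recovered code cannot be reached. The AE listings therefore cannot show, in the outcome entry, a non-resolving event in a surviving patient. This is firm for non-serious, unrelated events open at the 5-10 day visit. For device effects and SAEs it depends on whether the code is updated after later follow-up, which the documents leave open.

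The effect is limited to a listing item. No AE, SAE or death count changes, and no planned table uses outcome as a summary variable. How many events would be affected cannot be stated, since no event counts are given. The conclusion assumes that investigators apply Table 9 as written and that no eCRF instruction outside these documents overrides it.

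Table 8 is a secondary point. It mixes severity with outcome and leaves gaps in both directions. No bias is demonstrated.

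**What to change.** In Table 9, define the two codes by the state of the event at last observation:

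- *Recovering/Resolving*: ongoing but improving.
- *Not recovered/Not resolved*: ongoing and unchanged or worse, whatever the reason the patient's study ended.

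Add to Section 7.2 that the outcome code is updated after post-study follow-up of adverse device effects and SAEs.

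In Table 8, grade by functional impairment alone. Sequelae would be dropped from Severe, and their absence from Moderate. No information is lost, because Table 9 already records sequelae as an outcome.

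The cost is a wording change in two tables, one sentence in Section 7.2 and matching eCRF completion instructions. No new visit is needed; the direction of an open event is a judgement that the investigator can make at assessments already planned. The downside for the sponsor is that the AE listings may look slightly less favourable.

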### 7.2.1 Adverse Event of Special Interest

Adverse events of special interest are listed below. The adverse events within this section represent those that are thought to have an association with the use of the AMIA APD Solution Generation System or in conjunction with performing the peritoneal dialysis procedure.

- Aseptic Peritonitis
- Hypovolemia
- Hypokalemia
- Hyponatremia
- Encapsulating Peritoneal Sclerosis
- Medication Error: administration of incorrect glucose concentration
- Lactic Acidosis

- Hyperglycemia
- Hypocalcemia

The definitions of AESIs are provided in [Appendix 5](#).

### **7.2.2 Medical Events Commonly Associated with Peritoneal Dialysis**

The medical events and their definitions, that have been commonly reported as possibly related to PD therapy in general, are provided in [Appendix 6](#). This list has been provided to ensure these events are captured in the patients' medical history, when appropriate. If an event is part of the patient's medical history, it will not be considered as an AE for the study unless the frequency increases or the severity worsens.

### **7.2.3 Adverse Events Reporting**

The PI shall:

- Record every AE with a full description.
- Follow-up or new information about an SAE should be provided by the Investigator or a designee using the SAE form within 24 hours of becoming aware of the new information.
- All non-serious AEs that are upgraded to an SAE should be forwarded to Baxter or designee within 24 hours.
- Supply Baxter or designee, upon Baxter's or designee's request, with any additional information related to the safety reporting of a particular event.
- Report any SAE if becoming aware after study completion has occurred in a patient during their participation in the study, the SAE must be reported on the SAE Form within 24 hours of awareness.
- If an event is part of the patient's medical history, it will not be considered as an AE for the study unless the frequency increases or the severity worsens.

### **7.3 Product Complaints**

A product complaint is any written, electronic, or oral communication that alleges deficiencies related to the identity, quality, durability, reliability, usability, safety, effectiveness, or performance of a product after it is released for distribution or related to a service that affects the performance of such product. A complaint may involve the possible failure of the product itself, its packaging, or its labeling (i.e., product label,

---

package insert, or any instructions for use). The complaint need not be confirmed by the manufacturer to be considered a complaint. Any product complaints identified by the investigator will be reported to Baxter using a paper Product Complaint/Non-Medical Complaint Form.

#### **7.4 Medical Monitor**

The medical monitor will regularly review data collected from eCRFs, and laboratory data for potential safety concerns. This review plan will be documented in a study Safety Management Plan.

Periodic review of reported AEs will be completed by Baxter or designee. At the site level the Investigator must assess risk and clinical significance of events to each individual study patient, including removing the patient from the study if necessary.

#### **7.5 Safety Reporting to Authorities and Institutional Review Board**

It is the responsibility of the Investigator to report any SAEs to IRB according to local regulatory requirements

Baxter or designee will assess each SAE reported by the Investigator to determine if the event qualifies as an Expedited Report according to local regulations. Expedited reports will be submitted to the appropriate Authority by Baxter or designee. Per regulations, Investigators will receive a letter from Baxter or designee describing the expedited SAE. The Investigator should file this letter within their Investigator Site File. Additionally, the Expedited Report letter may need to be submitted by the Investigator to their IRB, as appropriate per local regulations.

#### **7.6 Pregnancy Reporting**

If a female study patient or a study patient's partner becomes pregnant during the study patient's participation in the trial, the pregnancy must be reported to the Sponsor by providing a completed Pregnancy Report Form and Pregnancy Follow-up Form to Baxter Global Patient Safety ([REDACTED]).

### **8. STUDY ACTIVITIES**

#### **8.1 Schedule of Evaluations and Procedures**

All clinical study evaluations will be performed according to [Appendix 1](#) and the instructions listed below. If a patient discontinues from the study prematurely, every attempt will be made to perform all of the procedures and evaluations that are scheduled for the final visit (i.e., End-of-Study/ Early Termination Visit).

---

[REDACTED]

---

## 8.2 Screening Period (approximately 3 weeks)

Consented patients who have met the study entry criteria will be allowed to continue their participation in the study and will undergo the Screening assessments and home evaluation.

The following procedures should be completed during the Screening Period:

1. Patients and care partners (if participating) (See Section 5.4.1) sign the ICF on the first day of the Screening Period.
  2. Record patient medical history (PD history including the APD prescription per day, history of peritonitis and other disorders or diagnosis). Medical history will also include demographics (age, gender, race, height, weight, body mass index calculated as weight (kg)/height (m), and ethnicity) and prior medications (all medications being taken at the time of Screening and 30 days prior to Screening, with each medication having a corresponding indication recorded on the Medical History eCRF form).
  3. Physical examination including weight and height.
  4. The date of the last total Kt/Vurea calculation should be noted (if a total Kt/Vurea is available from within 45 days of Screening, then it will be used as the Screening/Baseline value [i.e., no urine and peritoneal effluent samples will be collected for total Kt/Vurea]).
  5. Clinical laboratory evaluations as outlined in [Appendix 2](#).
  6. Vital signs including BP, pulse rate and temperature.
  7. Home suitability assessment.
  8. Feed water analysis for the home.
  9. Home Installation, when suitable.
  10. The PI or designee will assess each patient at the Screening visit and on a weekly basis, according to standard of care. At a minimum, this assessment will include evaluation of BP, pulse rate, weight, fluid status and dialysis prescription.
  11. Collection of concomitant medication information.
  12. Collection of AEs/ SAEs.
  13. The Investigator must assess the stability of the patient (Clinical and prescription stability).
-

14. If the patient is a screen failure, the reason for their failure must be recorded. Any patient who withdraws from the study before installation of the device is considered a screen failure. In addition, any patient who withdraws from the study after the installation but before confirming that all the inclusion criteria and none of the exclusion criteria are met, and withdraws due to a non-device related issue, is also considered a screen failure.

### **8.3 Training for PD Home Solution Generation System**

Study personnel performing training with the AMIA APD Solution Generation System for this clinical study will be comprised of physicians, PD nurses and other clinicians. Study staff will be trained on the use of the AMIA APD Solution Generation System by the Sponsor's representative prior to patient enrollment. Training dates and training material, provided by Baxter, will be documented and filed in the Investigator Site File.

### **8.4 Baseline Period (In-center Training Period)**

The Baseline Period (In-center Training Period) will begin immediately following the Screening Period, will include in-center training, and will last for approximately 2 weeks. The following information will be collected and procedures or evaluations will be performed:

1. Baseline Assessments
    - Assessment by an Investigator or a designee. At a minimum, this assessment will include evaluation of BP, pulse rate, weight, fluid status and dialysis prescription.
    - Collection of concomitant medication information.
    - Collection of AEs/ SAEs.
  2. Installation of the AMIA APD Solution Generation System in the patient's home (if not yet performed).
  3. AMIA APD Solution Generation System specific device training and general therapy training for the patient and care partner (if participating) (See Section [5.4.1](#)).
  4. Machine information including the available code number(s) and a lot/serial number(s) at initial installation and if the device or any of the disposables are changed.
- 
- 

5. Baseline Period (In-center Training Period) will conclude with:
  - Successful comprehension and retention testing, provided by Baxter, for the patient and/or care partner (if participating). If the patient does not read and understand English, the care partner will assist the patient with comprehension and retention testing.
  - The Investigator must reassess the stability of the patient during the Baseline Period (In-center Training Period). Once the clinician concludes that the patient is clinically stable and their PD prescription is stable, then the patient can begin treatment in the home.
  - Written confirmation of independent care by patient and care partner (if participating).

### **8.5 Each Treatment Day**

Patients will set up and complete a treatment using the AMIA APD Solution Generation System according to their prescribed dialysis regimen.

The following assessments will be completed each day throughout the Study Treatment Period.

1. Collection of concomitant medication information.
  2. Weight pre- and post-dialysis.
  3. Vital signs, before and after each treatment, including seated BP, pulse rate and temperature.
  4. Collection of AEs/ SAEs.
  5. Collection of ADEs and SADEs once the patient is connected to the AMIA APD Solution Generation System.
  6. Collection of AMIA APD Solution Generation System-related PCs/ DDs, which would include functional characteristics (e.g., particulate matter, PD fluid discoloration, leaks, tubing separations), will begin from the time of signing informed consent and will continue throughout the entire Study Treatment Period.
  7. Collection of machine information.
  8. Collection of machine observations.
  9. Chlorine testing performed by patients before each treatment.
- 
- 

10. Collection of diary source data (eDiary).

